Clinical benefits we anticipate involve reduced institutional cost and improved postoperative outcomes: 1) through an anticipated reduction in wound closure time, we expect a reduction in overall procedural time. The time related procedural cost is a established component affecting the overall cost of service provision. 2) a reduction in post-operative swelling, pain and irritation, through the elimination of the knot as well as reducing the amount of capillary action present.

These findings may be extended to other intraoral procedures including full dental clearances, other dentoalveolar and periodontal soft tissue procedures. Anecdotally, patients have re-presented post-operatively because of irritation from the knot. By reducing these additional visits from the cost variables involved in service delivery, it might be possible to make each unit of funding to the institution stretch further, benefiting more individuals.

Proposed methodology

Study design

The proposed research will be conducted as a split-mouth study comparing of postoperative outcomes (pain, swelling, wound healing) and intraoperative wound closure time between knotless and conventional sutures. The sites, left and right mandibular molars, will be randomised with regards to the proposed intervention. Third molar surgery to both left and right sides will be carried out at the same time.

Study setting/Location

It will be a multi-centre study carried out at the 1) outpatient procedural suite, Clinical Services Building, Faculty of Dentistry, University of Otago (UoO) and 2) oral surgery clinic, Southland Hospital Dental Unit, Southern District Health Board (SDHB).

Study population

Subjects will be invited to participate from a population of patients who have been referred from their primary care provider (general medical practice or general dental practice) for the removal of their mandibular third molars.

Recruitment of participants

Patients will be screened for suitability as part of regular oral surgery service provision at the School of Dentistry, UoO and Southland Hospital Dental Unit, SDHB. They will be assessed for suitability based on clinical findings and radiographic mandibular third molar impaction patterns. Approximately 20 participants will be recruited through the School of Dentistry and 50 through the Southland Hospital Dental Unit, to reflect the amount clinical time available to treat and review the patients at the different sites.

Eligibility criteria

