In this split-mouth study, the patients will receive the control, 3-0 vicryl rapide suture, on one side and the intervention ,3-0 V-loc suture, on the contralateral side.

The allocation of suture material to closure site, left or right third molar surgical site, will be drawn at random prior to the procedure. Allocation will be concealed through pre-sealed envelopes containing the side allocated the intervention. There will be an equal number of sealed allocations, of the intervention, to each site. The site receiving the intervention and the site receiving the control—left or right mandibular third molar—will be recorded in the patient's file. This will aid in ensuring a balanced number of interventions on each side.

Patients will be blinded as to which site receives the control (3-0 vicryl rapide) and which site receives the intervention (3-0 V-loc). However, as part of the consent process, patients will be made aware that both materials will be used.

Study procedure

Surgical procedure

The surgical removal of bilateral similarly impacted wisdom teeth will be performed by the primary investigator ([name]). All procedures will be supervised by a specialist oral and maxillofacial surgeon employed by the University of Otago, or, a senior dental officer at Southland Hospital. We aim to eliminate inter-operator variability and consequent performance bias by involving only a single operator. The surgical removal of the patient's third molars will be carried out at a separate appointment from the initial consultation. This allows the patient to have time to consider their participation in the study and whether they would like to defer of withdraw from the procedure.

Intravenous cannulation will commence following patient identification, confirmation of procedural consent and a 60 second pre-procedural 0.2% chlorhexidine gluconate mouthwash. The procedures will be carried out under intravenous (IV) sedation using midazolam which will be titrated to achieve the desired depth of sedation. Patients will have their height and weight (body mass) taken on the day. There will be a standardised pre-operative dose of 1.2g Amoxicillin/Clavulanic Acid, 8mg dexamethasone and 40mg parecoxib given to all participants. Patients that are allergic to penicillin antibiotics will be given a 1g dose of IV cefazolin; patients that are allergic to beta-lactam antibiotics will receive a 600mg IV infusion of clindamycin over 20 minutes.

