- 1. Eligible patients will be invited to participate and will be provided with a copy of the participant information sheet if they express interest. The initial appointment will involve a consultation with the clinician/primary investigator. If the patient provides informed consent to participate, they will then complete the pre-operative questionnaire. This questionnaire contains the Oral Health Impact Profile, OHIP-14 (Slade, 1997), Locker's Global Oral Health Item (Thomson et al., 2012), and the Dental Anxiety Scale (Corah, 1969).
- 2. Patients will be assigned a study participant number which will be used during data collection. This will be recorded separately from their clinical records. According to the applicable institutional protocol, the intervention site, material and batch number will be recorded in the patient's clinical record.
- 3. The type of third molar impaction according to the Winter's classification (mesio-angular, disto-angular, vertical, horizontal, transverse bucco-lingual, inverted) will be recorded for each participant. Clinically and radiographically similar impaction patterns are crucial in a split-mouth design.
- 4. Prior to the procedure, the patient will:
 - i. Complete a VAS score on pre-operative pain and irritation;
 - ii. Have a triplicate of baseline measurements to later aid in assessing facial swelling will be recorded.
 - iii. Have their height and weight taken.

The removal of the bilateral similarly impacted third molars will then commence under IV sedation.

5. The time taken for removal of the mandibular third molar from each side will be recorded, starting from the time of the initial incision to the completion of tooth removal. Both sites will be irrigated and inspected to remove and fine debris in the surgical site, ensure no remnants remain and there is no inadvertent damage to adjacent structures. The time taken for wound closure will also be recorded, starting from the time of the first bite of the soft tissue, to the time the sutures have been placed and the wound edges satisfactorily approximated.

- i. Prior to the procedure, the side receiving the intervention will be drawn.
- ii. This will be drawn at random, with the nurse and the clinician unaware of which side the intervention is assigned to until the envelope is opened.

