- 6. Participants will be asked to rate the pain and irritation experience at each side every 6 hours while awake for the first 48 hours. A non-graduated 100mm VAS, in the patient's post-operative diary will be included, for every waking 6 hour interval.
 - i. They will additionally record under the respective pages:
 - i. The time between the end of the procedure (will be written down into the booklet at the conclusion of the procedure) and the first use of rescue medication
 - ii. The amount of rescue analgesia consumed each day
 - iii. Any adverse events experienced post-operatively (e.g. vomiting, nausea, headaches, uncontrolled pain and swelling from the site)
- 7. Participants will be asked to attend a post-operative review with the primary investigator at 48h following their procedure, and again at 7 days.
 - i. A repeat triplicate of facial swelling measurements will be taken at each of these appointments.
 - ii. A post-operative questionnaire will be completed at each appointment. This contains items relating to post-operative pain, irritation at the sites, whether they needed to be reviewed in a community-based practice or at the institution in the intervening period, whether intervention was required, compliance with the prescribed pain relief, requirement for rescue analgesia, OHIP-14, Locker's global oral health measure. Additionally, the patient's perception of which side they felt was healing better will be recorded.

Measurement of facial swelling

Facial swelling will be determined by tape measurements between the tragus and soft tissue pogonion (A), tragus and lateral corner of the mouth (B), lateral corner of the eye and the angle of the mandible (C). Facial measurements will be calculated as: (A

+B+C)/3, and facial swelling (%) will be calculated as: [(postoperative measurement – preoperative measurement] × 100% (Baqain et al., 2012).

- 1. These measurements will be taken prior to commencement on the day of the procedure;
- 2. 48h post-operatively;
- 3. 7 days post-operatively.

Data entry

Data will be entered into a Microsoft Excel spreadsheet, recording the triplicate of facial measurements, the nature of impaction involved, the time taken to close the surgical site, the intervention side/site and scores from the operative questionnaires. The data will be checked for errors prior to de-identification and data analysis.

Statistical considerations and data analysis

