Sample size. Power analysis yielded a sample size of 63 participants based on a paired sample t-test analysis with alpha of 0.01, power of 0.9, and a moderate effect size (Cohen's d = 0.5). Previous research supports that moderate to large effect sizes can be expected for our key outcome, closure time (Durand, 2017; Zhu et al., 2017). Furthermore, a simulation study on the sample considerations of split mouth designs also indicated that a sample size of approximately 60 participants would be appropriate. 70 participants will be recruited to account for possible drop-out and data loss from participant protocol deviation.

Statistical approach. Statistical analyses will be conducted using the statistical programming language R. Our outcome variables, closure time, inflammation, and pain, will be modelled using separate mixed models Analyses of Variance (ANOVA) with suture type as a within-subjects variable and age, sex, ethnicity, smoking status, previous pericoronitis and dental anxiety score as between-subjects variables. In the case of inflammation, irritation and pain, we will use a repeated measures design to account for multiple follow-ups. A post-hoc polynomial comparison of follow-up outcomes by suture type will also be used to determine whether the trajectory of healing differed significantly between suture types. In all cases, we will use an alpha

of 0.01, more stringent than the traditional 0.05. Using a lower alpha allows us to be more certain of our findings and also implicitly controls for the multiple comparisons we are making across different outcome variables.

Bias and confounding

Bias

The patient is blinded to which side receives the intervention to minimise reporting bias. Handedness will be controlled for by allocating an equal number of interventions to each of the left and right sides through the randomly selected system of sealed envelopes drawn prior to the procedure. Uneven loss to follow-up or withdrawal may cause one intervention-control-side combination to be over-represented.

Modifiers

Age

Increasing age has been associated with increased procedural difficulty. We have excluded individuals 45 years or older to minimise the effect of age.

Peri-operative medications

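### Nothing in the protocol keeps the order of wound closure independent of the suture, or lists that order for recording, so a first/second effect could be read as a suture effect on closure time

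*Protocol*

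**What the plan says.** The Study design section of the protocol places both extractions in one session: "Third molar surgery to both left and right sides will be carried out at the same time". Under Surgical procedure there is one surgeon throughout: "We aim to eliminate inter-operator variability and consequent performance bias by involving only a single operator". One person cannot suture two wounds at once, so I read the first sentence as the same session, with one side closed first.

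The Randomisation section randomises suture to side and nothing else: "The allocation of suture material to closure site, left or right third molar surgical site, will be drawn at random prior to the procedure", with the balance stated as "There will be an equal number of sealed allocations, of the intervention, to each site". Under Bias, this balance is offered as control for handedness.

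Data collection, item 5, repeats the timing of the draw ("Prior to the procedure, the side receiving the intervention will be drawn") and limits concealment to the period before opening: "with the nurse and the clinician unaware of which side the intervention is assigned to until the envelope is opened". It does not say at what point in the session the envelope is opened. The same item times tooth removal and wound closure as durations. The Randomisation section has the patient's file show which side received which suture. The Data entry section names, among other fields, "the time taken to close the surgical site, the intervention side/site and scores from the operative questionnaires". None of these places names first or second position.

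The Statistical approach models closure time "with suture type as a within-subjects variable", together with patient-level covariates.

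**The concern.** A split-mouth comparison removes differences between patients. It does not remove differences between the two sides of one patient, and position in the closing sequence is such a difference. The second closure may be quicker or slower than the first because the operator has just worked in that mouth, is more tired, or is working at a different depth of sedation.

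Randomising suture to side protects against this only if order is chosen without regard to the suture. The protocol does not require that. The operator may know the allocation before choosing where to start. Even if the envelope were opened only at closure, which suture goes in first would remain a free choice. The two closures differ in technique (interrupted against continuous running), so a preference for placing one kind first is conceivable.

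Closure time is the most exposed outcome: it is the first primary objective, the outcome the sample size discussion calls key, and it is measured on an operator who cannot be blinded. If order does track suture and has not been captured, no later analysis can separate the two. The patient-level covariates in the model take the same value for both sides of a patient, so they cannot absorb an order effect.

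**Working it through.** **Inputs from the protocol (sample size paragraph).** Paired t-test, alpha 0.01, power 0.9, Cohen's d = 0.5, 63 patients needed, 70 recruited. Sidedness is not stated; two-sided is assumed.

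**Reproducing the stated figure.** Exact power comes from the noncentral t distribution with n − 1 degrees of freedom and noncentrality d√n. For n = 63, √63 = 7.937, the noncentrality is 0.5 × 7.937 = 3.97, the critical value is 2.657 and power is 0.901. For n = 62 power is 0.895. So 63 is the smallest sufficient n, and 63/(1 − 0.10) = 70. The stated figures reproduce.

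**Assumed inputs.** The protocol gives no order effect. Let g be the first/second difference in SDs of the within-patient difference, taken as 0.1, 0.2 and 0.3. Let p be the share of patients in whom one given suture is closed second.

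**Formulas.**
- Bias in the mean paired difference: g(2p − 1).
- SD of the paired difference: √(1 + 4p(1 − p)g²).
- Rejection rate with no true suture effect: noncentral t, 62 degrees of freedom, noncentrality (bias/SD) × √63.

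**Worked example, g = 0.2, p = 0.75.** Bias = 0.2 × 0.5 = 0.10. SD = √(1 + 0.75 × 0.04) = 1.015. Noncentrality = (0.10/1.015) × 7.937 = 0.78. Rejection rate = 3.5%.

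**Results, n = 63, nominal 1%.**

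| Order effect g | p = 0.5 | p = 0.75 | p = 1 |
|---|---|---|---|
| 0.1 SD | 1.0% | 1.6% | 3.6% |
| 0.2 SD | 1.0% | 3.5% | 15.1% |
| 0.3 SD | 1.0% | 7.3% | 39.8% |

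**Power at a true d of 0.5 when the order effect works against it** (0.90 with no order effect):

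| Order effect g | p = 0.75 | p = 1 |
|---|---|---|
| 0.1 SD | 0.81 | 0.70 |
| 0.2 SD | 0.68 | 0.40 |
| 0.3 SD | 0.52 | 0.15 |

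**Same side always first.** With suture split 35/35 between sides in 70 patients, the bias is zero. A simulation of 200,000 trials at g = 0.2 gave a rejection rate of 0.85%, so the test is not inflated.

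**The case against.** The strongest reply is that the bias needs two things the protocol does not show: that order follows the suture, and that order matters. This stands. An operator who always begins on the same side has order independent of suture under the existing randomisation, and the bias is then zero. The larger figures above need one suture to go second in every patient.

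Three stronger readings are tempting and are not supported.

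- A reader might infer that each wound is opened and closed before the other is opened. Data collection, item 5, has both sites irrigated and inspected between the removal and closure timings, so both teeth may be out before either closure. The order of operating and the order of closing need not agree, and an argument from how long a wound stood open has no fixed direction.
- A reader might take the Data entry list as proof that order will go unrecorded. That list is not complete: it also omits tooth-removal time, height and weight, and the diary scores, all of which are collected. If clock times rather than durations are kept, order could be recovered. What can be said is that order is nowhere named as an item.
- A reader might extend the point with equal force to pain and irritation. Both sides are done in one session and rated every six waking hours for 48 hours, so the offset between sides is only part of one procedure. No figure in the protocol supports a material effect there.

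It can also be said that an extra model term belongs in a statistical analysis plan, and that the protocol promises to handle confounders by modelling. The absence of the term is therefore no fault in itself. But an analysis plan can use closure position only if it has been captured, and both the capture and the rule for choosing order are matters of conduct that the protocol should fix.

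**Conclusion.** The point holds in a conditional form. One operator closes both wounds in one session, only suture-to-side is randomised, and the protocol neither makes closure order independent of the suture nor names it for recording. If order follows the suture, a first/second effect on closure time is indistinguishable from a suture effect. Over assumed order effects of 0.1 to 0.3 SD, the false-positive rate rises from 1% to between 1.6% and 7.3% under partial tracking (75%), and to between 3.6% and 39.8% under complete tracking. If order is independent of the suture it stays at about 1%. These figures rest on n = 63, a two-sided test and an order effect that the documents do not supply. They show what the gap allows, not what will happen. Priority is low to moderate: the bias may well be zero, but as written nobody could demonstrate that.

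**What to change.** - **Conduct.** Have the operator write down which side will be closed first before the envelope is opened, or set closure order by any rule that ignores the suture. This does not dictate which side goes first, and the operating order need not be tied to the closing order.
- **Recording.** Enter first or second closure for each side on the theatre form and in the data sheet.
- **Analysis.** Include closure position as a within-patient term for closure time. For the diary outcomes, use it in a sensitivity analysis only.

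The cost is one sentence, one data field and one degree of freedom. The sample size of 63, with 70 recruited, is unchanged, and no extra staff are needed.

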Inclusion Criteria

- 1. Patients referred for third molar removal from a primary care provider
- 2. Patients who volunteer participation
- 3. Patients may be either male or female
- 4. The patient has been screened by the primary investigator or supervising specialist for suitability to participate in the study
- 5. Are aged between 18 and 44 years
- 6. Are able to understand verbal and written instructions.
- 7. Present with bilateral similarly impacted mandibular third molars as determined using Winter's (1926) classification system , requiring surgical removal
- 8. Are able to tolerate outpatient oral surgery under local anaesthetic and intravenous sedation
- 9. ASA l or ll
- 10. The patient has provided informed consent regarding:
 - a. Participation in the study
 - i. The use of knotless sutures in the closure of the surgical wound
 - b. Surgical removal of third molars under local anaesthetic and intravenous sedation

Exclusion Criteria

- 1. American society of anaesthesiologists (ASA) physical classification¹ III or IV
- 2. Polypharmacy (\geq 5) medications²
- 3. \leq 17 years, \geq 45 years
- 4. Patients contraindicated to undergo surgical third molar removal
- 5. Opioid and illict drug addiction
- 6. Patients who have allergies or contraindications to the procedural usage of:

¹ Abouleish, A. E., Leib, M. L., & Cohen, N. H. (2015). ASA Provides Examples to Each ASA Physical Status Class. ASA Newsletter, 79(6), 38–49.

² Masnoon, N., Shakib, S., Kalisch-Ellett, L., & Caughey, G. E. (2017). What is polypharmacy? A systematic review of definitions. BMC geriatrics, 17(1), 230. https://doi.org/10.1186/s12877-017-0621-2

- a. midazolam
- b. dexamethasone
- c. parecoxib
- d. paracetamol
- e. ibuprofen
- f. co-amoxiclav
- g. cefazolin
- h. clindamycin
- i. chlorhexidine
- 7. The presence of symptomatic pericoronitis.
- 8. The presence of other pathology in the oral cavity.
- 9. Patients with poor oral hygiene (plaque >1/3 of tooth surface).
- 10. Pregnant or lactating women.
- 11. Patients unwilling to remove facial hair for the purpose of facial measurements in order to assess swelling.
- 12. Patients who are unable to give informed consent.
- 13. Patients who decline participation.
- 14. Patients who are unable to attend the required follow-up appointments.
- 15. Patients who are unable to comprehend directions and instructions.

Randomisation

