Dexamethasone is part of the current peri-operative protocol for IV sedation to maintain patient comfort. Omitting this medication may increase intraoperative pain levels and post-operative swelling during the immediate period. However, it is likely to exert some effect on the immediate post-operative pain measures during the immediate post-operative window.

Post-operative pain relief

The benefits of paracetamol in conjunction with ibuprofen in relation to postoperative pain management following third molar surgery has been previously established in the literature (Best et al., 2017). The effectiveness of post-operative pain relief will likely have a global influence on the reported pain scores, likely modifying the study results. However, due to the multifactorial nature of pain, certain patients may perceive an improvement in pain control from weak-opioids such as codeine, in spite of the literature suggesting otherwise.

Alveolar osteitis and post-operative infection

Dry socket or alveolar osteitis is a common post-operative complication associated with tooth extraction, particularly third molar surgery. The hypothesis is that premature fibrinolysis occurs due to the nature of the patient's intraoral flora, particularly smokers, that may predispose them to this. Patients that have had previous or recent bouts of pericoronitis will also likely have unfavourable bacterial microenvironments within the surgical site. 0.2% chlorhexidine mouthwash will be used pre-operatively as well as an IV dose of 1.2g co-amoxiclav. Symptoms are generally reported between day 3-5 following extraction, hence our main data collection points avoid this window.

Confounders

Confounding variables will be addressed through statistical means and modelling techniques at the time of data analysis.

Ethical approval and Māori approval

Ethical approval

Approval pending, application in process. Universal Trial Number (UTN) U1111-1259-5457

Māori consultation

Completed with approval

Funding

This research is funded through a Sir John Walsh Research Institute Fuller Scholarship grant.

Payment for treatment

Patients will bear the cost of treatment according to the fee schedules outlined at the respective institutions.

Selected references

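### Previous pericoronitis is described as acting at the surgical site but is modelled once per patient and not listed for collection by side, so the split-mouth comparison cannot adjust for one-sided disease

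*Protocol*

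**What the plan says.** Exclusion criterion 7 is "The presence of symptomatic pericoronitis". It does not cover resolved or recent bouts.

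The Modifiers section on alveolar osteitis and post-operative infection explains why past disease matters: "Patients that have had previous or recent bouts of pericoronitis will also likely have unfavourable bacterial microenvironments within the surgical site".

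The Statistical approach describes mixed-model ANOVAs with "suture type as a within-subjects variable and age, sex, ethnicity, smoking status, previous pericoronitis and dental anxiety score as between-subjects variables".

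The two sides are matched on impaction pattern: patients must "Present with bilateral similarly impacted mandibular third molars as determined using Winter's (1926) classification system".

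The Data collection section lists the content of the pre-operative questionnaire (OHIP-14, Locker's item, Dental Anxiety Scale) and the Winter class. The Data entry section lists facial measurements, impaction, closure time, intervention side and questionnaire scores. Neither lists pericoronitis by side or by date.

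Under Randomisation, the side that receives each suture, "left or right third molar surgical site, will be drawn at random prior to the procedure", is concealed in sealed envelopes, with equal numbers for left and right.

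**The concern.** The protocol's reason for including the variable and the way it includes it are at different levels. The reason concerns the site; the model term concerns the patient. A patient with a recent bout on the left and none on the right gets the same code as a patient affected on both sides, although only in the first do the two halves of the pair differ.

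Pain, swelling and irritation are primary objectives, and they are the outcomes that local infection would plausibly move. If one-sided disease is common and its effect is large, it adds noise to each paired difference, and in a given sample it may fall more often on one suture than on the other. The planned term corrects neither. If side is never recorded, a later analysis plan cannot correct them either.

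**Working it through.** **1. Why the planned term cancels.** For patient *i* and side *s*, write the outcome as

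Y_is = μ + τ·T_is + β·P_i + γ·L_is + u_i + ε_is

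Here T is suture type (1 = knotless), P is the per-patient pericoronitis code, L is disease history at that site, and u is the patient effect. The knotless-minus-conventional difference is

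D_i = τ + γ·(L_i,knotless − L_i,conventional) + (difference of the two ε terms)

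P_i and u_i drop out. The term in γ is 0 when neither or both sides are affected, and +γ or −γ when one side is. A suture-by-P interaction would not help, because P_i does not say which side was affected, so the sign stays unknown.

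**2. The plan's own figure.** Inputs from the Sample size paragraph: paired t-test, alpha 0.01, power 0.9, d = 0.5. Sidedness is not stated. With the noncentral t distribution and two-sided alpha, n = 62 gives power 0.895 and n = 63 gives 0.901, so the stated 63 is reproduced. One-sided alpha would give 55. If all 70 recruits are analysed, power is 0.934.

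**3. Bias and type I error.** Suture side is random, so +γ and −γ are equally likely and the γ term has mean zero. A simulation of 100,000 trials with N = 63 agrees. Here q is the share of patients with one-sided disease and e is its effect in SDs of the paired difference among other pairs.

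| q | e | Mean bias (SD) | Type I error |
|---|---|---|---|
| 20% | 0.5 | 0.0005 | 0.0105 |
| 30% | 1.0 | −0.0002 | 0.0099 |

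**4. Precision.** The variance of the paired difference becomes 1 + q·e². The part due to one-sided disease, which an ideal side-level covariate could remove, is q·e²/(1 + q·e²). The protocol gives neither q nor e, so both are assumptions (q from 10% to 30%, e from 0.25 to 1.0). The last two columns apply only if d = 0.5 refers to pairs without one-sided disease, so that d becomes 0.5/√(1 + q·e²).

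| q | e | q·e² | Variance share | d | Power at n = 63 |
|---|---|---|---|---|---|
| 10% | 0.25 | 0.00625 | 0.6% | 0.498 | 0.899 |
| 20% | 0.5 | 0.05 | 4.8% | 0.488 | 0.884 |
| 10% | 1.0 | 0.10 | 9.1% | 0.477 | 0.866 |
| 20% | 1.0 | 0.20 | 16.7% | 0.456 | 0.829 |
| 30% | 1.0 | 0.30 | 23.1% | 0.439 | 0.791 |

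**5. Chance imbalance in one trial.** The SD of its contribution to the mean difference is e·√(q/N). This is 0.5·√(0.2/63) = 0.028 and 1.0·√(0.3/63) = 0.069, in SDs of the paired difference. For comparison, the standard error of the mean difference without this source is 1/√63 = 0.126.

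**The case against.** The strongest reply is randomisation. A reader might infer that one-sided disease confounds the suture comparison. The documents do not support that: concealed random allocation with equal left and right numbers makes it noise, as step 3 shows. This part of the reply stands in full.

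A reader might also infer that 63 is too few. That is not supported either. In a paired t-test, d is the mean difference over the SD of the paired differences, and in eligible patients that SD would already include side-to-side heterogeneity. Nothing in the protocol says that d = 0.5 comes from disease-free pairs. The sample-size paragraph also names closure time as the key outcome, and past pericoronitis has no stated link to it. The power column is therefore a pessimistic reading; the variance share does not depend on this.

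A third inference is that patients who become ineligible between visits will be treated, because "The surgical removal of the patient's third molars will be carried out at a separate appointment from the initial consultation" and no second eligibility check is described. This rests on silence. Criterion 7 is not tied to the screening visit. The sentence "Intravenous cannulation will commence following patient identification, confirmation of procedural consent and a 60 second pre-procedural 0.2% chlorhexidine gluconate mouthwash" covers only what precedes cannulation; a baseline VAS and facial measurements are also taken before surgery.

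Those baselines do capture some active disease. Facial measurements are taken for each side and swelling is calculated from them as a change. The baseline VAS is not said to be per side. Neither would reliably identify a resolved bout, which is what the Modifiers section describes.

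Finally, covariate coding often belongs in the analysis plan, and the protocol leaves confounders to modelling at analysis. That is fair for the coding. But the protocol already fixes this variable as between-subjects, and no analysis plan can use side and date if they were not collected.

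**Conclusion.** The point holds as a modest one about precision and model specification. The protocol names a site-level factor, then models it in a form that cannot act on the within-patient comparison, and does not list the data needed to do better.

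There is no expected bias, no type I error inflation and no error in the sample size of 63. The cost is forgone precision and unadjusted chance imbalance for pain, swelling and irritation. Its size cannot be determined from the protocol. Under the assumed ranges it runs from negligible (0.6% of the paired variance) to moderate (23%).

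This rests on two assumptions: that some enrolled patients have one-sided history, and that side and date are not captured on a form that the protocol does not describe.

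**What to change.** 1. On the pre-operative form, record pericoronitis history separately for the left and right mandibular third molar, with the date of the last bout on each side.
2. In the mixed models for pain, swelling (taken here to be what the Statistical approach calls inflammation) and irritation, replace the between-subjects term for previous pericoronitis with a side-level, within-subject covariate. Fix its coding, including how recency is used, before outcome data are examined.

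The cost is one history field per side, which depends on patient recall, and one model term. Imperfect recall would reduce the gain in precision. Because history is taken before allocation, error in it should not favour either suture. Eligibility, allocation and sample size need no change on this account.

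The record has to be made prospectively, since side and date of past bouts may not be recoverable once the trial is complete.
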